(2) Construction and Multi-level Clinical Validation of Treatment Response Prediction Model

This is the core part of the study. Based on the quantified tumor immune microenvironment features output by the above model, combined with imaging data and essential clinical variables (such as TNM stage, Child-Pugh liver function classification and AFP level), a classification model will be built to predict patients' responses to four types of postoperative adjuvant therapy regimens: surgery alone, surgery combined with TACE, surgery combined with TACE plus systemic therapy, and surgery combined with systemic therapy alone. A strict hierarchical validation strategy will be adopted in this part.

Model Training Phase

Retrospective data from our center (n=1500) will be used. Inclusion criteria for patients in this phase: ① Histopathologically confirmed HCC; ② Underwent curative surgical resection; ③ Complete preoperative contrast-enhanced CT/MRI images, records of postoperative adjuvant therapy and follow-up data are available. Definition of treatment response: The primary endpoint is Relapse-Free Survival (RFS), and secondary endpoints include Overall Survival (OS) and Objective Response Rate (ORR). Multi-category machine learning algorithms (such as Gradient Boosting Decision Tree and Deep Neural Network) will be used for model training to output the most beneficial treatment regimen for each patient.

Internal Validation Phase

An independent validation set (n≈500, no overlap with the training set) will be randomly divided from the data of our center for preliminary evaluation of the model's discriminative performance and hyperparameter tuning to prevent overfitting.

External Validation Phase 1 (Retrospective Validation and Model Calibration)

Retrospective data (n=3000) will be collected from 8 to 10 medical centers nationwide. The main purposes of this phase are: ① To validate the model performance on larger and more heterogeneous external datasets; ② To calibrate or slightly optimize the model according to

validation results and finalize the predictive model.

External Validation Phase 2 (Large-scale Retrospective Validation)

The finalized model will be tested on a brand-new large-scale retrospective dataset (n=10,000) from 3 to 5 medical centers to further enhance the level of evidence and provide a solid basis for prospective studies.

(3) Study Population

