3.3 Evaluation Index System (Algorithm Performance, Clinical Utility, System Stability)

This study comprehensively evaluates the overall value of the AI model from three dimensions: algorithm performance, clinical utility and system stability.

Evaluation of Algorithm Performance

Conducted mainly during model development and validation, quantitative indicators are used to objectively assess the accuracy and robustness of the tumor immune microenvironment identification model and treatment response prediction model.

For the tumor immune microenvironment identification model: At the pixel level, Dice Similarity Coefficient (DSC) is used to evaluate the coincidence degree between segmentation results and expert annotations, and Intersection over Union (IoU) is adopted as a supplementary indicator. At the regional level, Precision, Recall and F1-Score are used to evaluate the recognition performance of specific components in the immune microenvironment.

For the treatment response prediction model: Area Under the Receiver Operating Characteristic Curve (AUC-ROC) is used to evaluate the binary classification ability of the model, and macro-average and micro-average AUC values are calculated. Accuracy, Precision, Recall and F1-Score calculated based on the confusion matrix are used to evaluate the performance of multi-classification tasks. Calibration Curve and Brier Score are used to assess the accuracy of predicted probabilities.

Evaluation of Clinical Utility

Conducted in the prospective study phase, focusing on evaluating the actual impact of the model on clinical decision-making and patient prognosis.

Primary clinical endpoints: Relapse-Free Survival (RFS), defined as the time from randomization to tumor recurrence or death from any cause. The Kaplan-Meier method is used for survival analysis, the Log-rank test is adopted for inter-group comparison, and the Hazard Ratio (HR) and its 95% confidence interval are calculated. Overall Survival (OS), defined as the time from randomization to death from any cause, is analyzed using the same statistical methods.

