Secondary clinical endpoints: Treatment decision change rate, calculated as the proportion of cases where AI recommendations are inconsistent with physicians' initial treatment plans. Physician adherence, defined as the proportion of physicians in the intervention group who finally follow AI recommendations. Decision Curve Analysis (DCA) is used to evaluate the clinical net benefit of the model, and standardized net benefit values under different threshold probabilities are calculated. A 1–5 point Likert scale is used to assess changes in physicians' decision confidence.

Evaluation of System Stability

Focusing on the operational performance and reliability of the AI system in real clinical settings.

Technical performance indicators: Inference speed, recording the average time and standard deviation for processing a single whole-slide image. System availability rate, calculated as: $\text{Availability Rate} = (1 - \text{Downtime} / \text{Total Operating Time}) \times 100\%$. Concurrent processing capability, testing the system performance when processing multiple requests simultaneously. API response time, monitoring the communication delay of the interface connected to the hospital

information system.

Usability evaluation: The System Usability Scale (SUS) is adopted, which contains 10 items with a 5-point Likert scale. The total score is converted into a percentage for evaluation. Task completion rate test is conducted to record the success rate of users completing specific operations within the specified time.

Reliability evaluation: Long-term monitoring of relevant indicators including Mean Time Between Failures (MTBF) (the average time for continuous normal operation of the system) and Mean Time To Repair (MTTR) (the average time for system recovery after failure). Error rate statistics are performed to classify and record various system errors and their occurrence frequencies.

All evaluation results will be summarized into a comprehensive evaluation report to support model optimization and clinical application. Data collected during the evaluation will be stored in a dedicated database to facilitate subsequent in-depth analysis. A systematic evaluation system ensures that the artificial intelligence model meets clinical application standards in terms of accuracy, practicality and reliability.

3.4 Sample Size Calculation (Description of Parameter Sources and Calculation Tools for Sample Size)

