3.4.2 Sample Size for Prospective Study Phase

(1) Sample Size for Prospective Observational Validation ($n = 1,000$)

Estimation Basis: This phase evaluates the correlation strength between model predictions and real clinical prognosis (C-index) using sample size formulas for survival analysis. Relapse-Free Survival (RFS) is taken as the primary endpoint.

Assuming the 12-month RFS rate of the control group is 60% and the corresponding HR of the model-consistent group is 0.7, a total of 256 events are expected. Simulated by PASS 2021 software, more than 300 events can be observed in 1,000 cases within a 24-month study period (12 months for enrollment + 12 months for follow-up), which meets the requirements of statistical power and supports stratified analysis.

(2) Sample Size for Prospective Interventional Study

Estimation Basis: This phase is a Randomized Controlled Trial (RCT) with strictly calculated sample size, taking RFS as the primary endpoint.

Sample size formula for Log-Rank test is adopted with the following parameter settings: Baseline event rate: The 12-month RFS rate of the standard treatment group (Arm B) is 65%. Effect size: The 12-month RFS rate of the AI-assisted decision-making group (Arm A) is increased by an absolute value of 10% (up to 75%), corresponding to $HR = 0.67$. Significance level (α): 0.05. Statistical power ($1-\beta$): 80% (conventional standard for RCT). Accrual time: 18 months. Follow-up time: 12 months. Dropout rate: 10%.

Calculated by PASS 2021 software, a total of 200 events are required. Considering the dropout rate, the total required sample size is 600 cases (300 cases in each group). This sample size can detect the clinical difference corresponding to $HR = 0.67$ and meet the power requirements under follow-up and dropout conditions.

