Data governance organizational structure: A data governance committee is set up to formulate data management policies. Dedicated data administrators are assigned to be responsible for daily data management. A data quality supervision team conducts regular data quality inspections. All researchers are required to receive and pass data management training to ensure the implementation of standardized data management.

3.7 Adverse Events (Specific Definition, Classification, Reporting Methods and Treatment Measures for Adverse Events/Serious Adverse Events)

Adverse events in this study refer to any negative medical outcomes related to AI-assisted decision-making, which are divided into three grades:

Grade 1 (Mild): AI recommendations lead to minor inconvenience or reversible additional examinations without long-term impacts;

Grade 2 (Moderate): AI recommendations result in inappropriate treatment regimens, which require medical intervention for correction without permanent damage;

Grade 3 (Severe): AI recommendations lead to misdiagnosis and mistreatment, causing permanent functional damage or significant shortening of survival time.

Once an adverse event occurs, the clinical center shall report it to the research safety monitoring committee through the online system within 24 hours. The committee consists of experts in hepatology, oncology, pathology and medical ethics. Treatment measures include immediately suspending the use of the AI system, organizing experts to assess the cause of the event, determining the correlation with the AI system, and formulating corrective measures. All adverse events will be fully recorded and included in the final research report.

3.8 Statistical Analysis Plan (Methods for Missing Data Processing, Definition and Selection of Statistical Analysis Datasets, Statistical Methods for Comparing Primary and Secondary Outcome Indicators, Algorithm Stability Evaluation)

R (Version 4.2.0), Python (Version 3.9) and SPSS (Version 26.0) software will be used for all statistical analyses. All statistical tests are two-sided with a significance level of $\alpha=0.05$.

Missing data processing: Multiple imputation method is adopted. For continuous variables, the Multiple Imputation by Chained Equations (MICE) is used to create 5 imputed datasets for combined analysis. Mode imputation is applied for categorical variables. The missing data mechanism will be tested: Complete Case Analysis is adopted for data Missing Completely at

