Random (MCAR); multiple imputation is used for data Missing at Random (MAR); selection models are applied for data Missing Not at Random (MNAR). Sensitivity analysis is conducted to compare results obtained by different missing data processing methods.

Definition of statistical analysis datasets:

Full Analysis Set (FAS): Includes all randomized patients who received at least one efficacy assessment, analyzed according to the Intention-To-Treat (ITT) principle.

Per-Protocol Set (PPS): Includes patients who fully complied with the research protocol, excluding patients with major protocol violations.

Safety Set (SS): Includes all patients who received at least one treatment, used for safety evaluation.

Primary analysis is based on the FAS, and the PPS is used for sensitivity analysis to verify the robustness of results.

Statistical methods for primary outcome indicators: For categorical variables (such as treatment response grouping), weighted F1-score and macro-average AUC are taken as main evaluation indicators, and Cohen's Kappa coefficient is used to assess the consistency between model predictions and actual clinical conditions. For survival data (RFS and OS), the Kaplan-Meier method is used to draw survival curves, the Log-rank test is used for inter-group comparison, and the Cox proportional hazards regression model is established to calculate the Hazard Ratio (HR) and its 95% confidence interval while adjusting for potential confounding factors such as age, gender and TNM stage.

Statistical methods for secondary outcome indicators: Decision Curve Analysis (DCA) is used to evaluate the clinical net benefit of the model. Calibration Curve and Brier Score are used to assess the accuracy of predicted probabilities. Repeated-measures Analysis of Variance is used for inter-group comparison of continuous variables. The Mann-Whitney U test is adopted for ordinal variables such as physician adherence and decision confidence scale scores.

Algorithm stability evaluation: Bootstrap sampling (1,000 repetitions) is used to calculate the 95% confidence interval of model performance indicators for stability assessment. SHapley Additive exPlanations (SHAP) values are used to analyze feature importance and improve model interpretability. Intraclass Correlation Coefficient (ICC) is calculated to evaluate the consistency of the model across different centers; $ICC > 0.75$ is regarded as good consistency.

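### RFS and OS are both named primary endpoints of the RCT and each tested at 0.05, but the trial is sized on RFS alone; if either may count as success, the false-positive risk is about 7–10%, not 5%

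*Protocol*

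**What the plan says.** **Section 3.3, Evaluation of Clinical Utility.** The primary list opens with RFS: "Primary clinical endpoints: Relapse-Free Survival (RFS), defined as the time from randomization to tumor recurrence or death from any cause". The same paragraph then adds OS: "Overall Survival (OS), defined as the time from randomization to death from any cause, is analyzed using the same statistical methods". Both are timed from randomisation, so both belong to the randomised trial. The secondary list starts afterwards, "Secondary clinical endpoints: Treatment decision change rate, calculated as the proportion of cases where AI recommendations are inconsistent with physicians' initial treatment plans", and continues with adherence, decision curve analysis and physician confidence. OS is not in it.

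**Section 3.8, Statistical Analysis Plan.** The paragraph on methods for the primary outcome indicators handles the two endpoints together: "For survival data (RFS and OS), the Kaplan-Meier method is used to draw survival curves, the Log-rank test is used for inter-group comparison". The level is set once for everything: "All statistical tests are two-sided with a significance level of" 0.05.

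**Section 3.4.2, Prospective Interventional Study.** The trial has a "strictly calculated sample size, taking RFS as the primary endpoint", in the singular. The inputs are alpha 0.05, 80% power, 12-month RFS of 65% against 75% (HR 0.67), 18 months of accrual, 12 months of follow-up and 10% dropout. The results are 200 events and 600 patients. No effect size or number of deaths is given for OS.

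**The concern.** Sections 3.3 and 3.8 describe a trial with two primary endpoints, and section 3.4.2 describes a trial with one. The number of primary endpoints decides how the 5% error is spent, so the two descriptions cannot both stand. As written, a report could present the trial as positive on RFS, on OS, or only on both, and each could be defended from the text. The trial is meant to supply high-level evidence that the model is clinically useful, so the rule for a positive result should be fixed before any outcome data by arm are seen.

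**Working it through.** **1. Does the stated event count use the whole 0.05 for RFS?**

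Inputs, all from section 3.4.2: HR 0.67, alpha 0.05, power 80%, 1:1 allocation (300 per group). The two-sided reading comes from section 3.8.

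- Implied HR: ln(0.75) / ln(0.65) = 0.668, which agrees with 0.67.
- Schoenfeld: 4 × (1.960 + 0.842)² / (ln 0.67)² = 4 × 7.849 / 0.1604 = 195.8, so 196 events.
- Freedman: (1.960 + 0.842)² × (1.67 / 0.33)² = 7.849 × 25.61 = 201.0, rounded up to 202 events.
- One-sided versions give 155 to 159 and do not fit.

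The stated 200 is reproduced at the full two-sided 0.05 on RFS. No alpha is left over for a second primary endpoint.

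**2. RFS power at 200 events**

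√200 / 2 × 0.4005 − 1.960 = 0.872, and Φ(0.872) = 80.8%. Testing OS as well does not change this figure.

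**3. If either endpoint counts as success**

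The chance of at least one false positive when neither endpoint differs is 1 − P(|Z₁| ≤ 1.96 and |Z₂| ≤ 1.96), with Z₁ and Z₂ bivariate normal. At correlation 0 this is 1 − 0.95² = 9.75%. The documents give no correlation between the RFS and OS tests, so the values below are assumptions.

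| Assumed correlation | At least one false positive |
|---|---|
| 0 | 9.75% |
| 0.3 | 9.5% |
| 0.5 | 9.1% |
| 0.7 | 8.3% |
| 0.8 | 7.8% |
| 0.9 | 7.0% |

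To see which rows are plausible, null trials were simulated with 600 patients, 65% 12-month RFS and 18 + 12 months. Further assumptions were 10% yearly dropout, 5–20% of RFS events being deaths without recurrence, and median survival after recurrence of 12 to 36 months. The correlations came out at about 0.42 to 0.67, which corresponds to 8.5% to 9.3%.

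**4. If both endpoints must succeed**

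The false-positive chance cannot exceed that of either single test, so it is at most 5%. The gap is then in power. The 80% applies to RFS only, and the power to win on both is not stated and cannot be derived, because no OS effect is given. As an illustration, if OS also had HR 0.67, about 196 to 202 deaths would be needed for 80% power on OS. The simulations in step 3 produced about 80 to 162 deaths, depending on the assumed survival after recurrence.

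**5. What each repair does**

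- RFS sole primary, OS tested only after RFS is significant: error 5%, and the 200 events stand.
- Both primary at 0.025 each: Schoenfeld 4 × (2.241 + 0.842)² / 0.1604 gives 238 events, and Freedman gives 244. With 200 events, RFS power is Φ(2.832 − 2.241) = 72.3%.

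**The case against.** The strongest reply is that section 3.4.2 is the only place that states the trial's primary hypothesis, and it names RFS alone. On that reading the error of the primary claim is 5%, and OS sits under the primary heading only through loose drafting. It can be added that multiplicity rules are often left to a separate statistical analysis plan, and that section 3.8 says conclusions will not rest on p-values alone.

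Part of this stands. No sentence says that a win on either endpoint is enough, so the inflated error is conditional. Independence is a bound rather than a realistic case, since deaths count in both endpoints. Loose drafting is a weaker explanation: OS is placed with the primary outcomes in two separate sections and is absent from the secondary list. The absence of an alpha split alone could be left to another document. The contradiction over which endpoints are primary could not, and the Protocol's own section 3.8 already sets the level for every test. The Lan-DeMets and O'Brien-Fleming text there concerns sample size re-estimation at an interim look and does not share alpha between endpoints. Restraint over p-values does not control error.

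A reader might infer three stronger points that the documents do not support:

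- *That the 80% power depends on RFS being the only primary endpoint.* It does not; step 2 gives 80.8% whether or not OS is tested. RFS power falls only if alpha is split, which the Protocol does not do.
- *That section 3.1 contradicts section 3.3 by saying* "secondary endpoints include Overall Survival (OS) and Objective Response Rate (ORR"). That sentence defines treatment response for the retrospective model-training phase, not for the randomised trial. The response rate it mentions is not in the trial's endpoint lists in section 3.3.
- *That the weighted F1-score and macro-average AUC in section 3.8 add further primary tests.* They are model-performance measures with no test attached, and they are not counted above.

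**Conclusion.** The inconsistency is explicit: two primary endpoints in sections 3.3 and 3.8, one in section 3.4.2, and the full two-sided 0.05 applied to each. Its effect depends on a success rule that the Protocol does not state. Under an either-endpoint rule the chance of at least one false positive is about 7–10% instead of 5%, for assumed correlations from 0.9 down to 0 and with no true effect on either endpoint. Under a both-required rule the error is controlled, but the planned power does not extend to OS. It would be too strong to say that the trial's error simply is 8–10%; that requires both the either-endpoint rule and a correlation below about 0.77.

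**What to change.** In sections 3.3 and 3.8, name RFS as the sole primary endpoint of the randomised trial, in line with section 3.4.2. Move OS to key secondary: tested at two-sided 0.05 only if RFS is significant, and otherwise reported as an estimate with its 95% confidence interval. The methods for OS and the sample size need no change. The cost is protocol wording, plus giving up any OS claim if RFS fails.

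If the sponsor wants OS to remain primary, a stated alpha split is also valid, but RFS then needs the 238 to 244 events of step 5, and OS needs its own effect and event assumptions. With exponential RFS at the section 3.4.2 rates, uniform accrual over 18 months and 12 further months of follow-up, the average event probability is about 0.457. The 540 patients left after 10% dropout (600 × 0.9) would then yield about 540 × 0.457 = 247 RFS events. The planned 600 could thus cover the RFS requirement, provided the analysis waits for those events. The single-primary version is simpler and matches the existing calculation.

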A total of 1,500 eligible surgical patients from our center will be enrolled and randomly divided into the model training set (n=1000) and internal validation set (n=500) at a ratio of 2:1, for model training, preliminary validation and optimization respectively. A total of 400 eligible patients have been enrolled so far, and the remaining 1,100 patients will be continuously recruited from the historical medical records of our center according to the inclusion and exclusion criteria.

A multi-center collaboration model will be adopted for external validation. ① External Validation

Set 1: A total of 3,000 retrospective cases from 8 to 10 domestic medical centers will be included for multi-center retrospective validation and model calibration, so as to verify the model's generalization ability across different institutions and conduct calibration or limited iterative optimization on the initial model. ② External Validation Set 2: A total of 10,000 retrospective cases from 3 to 5 large domestic medical centers will be included for the final test of the finalized model to fully evaluate its effectiveness and stability. Only forward validation will be performed on this dataset using the locked model without any parameter adjustment.

Part Two: Clinical Validation of Hepatocellular Carcinoma Adjuvant Therapy Prediction Model - Prospective Study

(1) Prospective Observational Study

A total of 1,000 eligible postoperative HCC patients will be consecutively enrolled from 10 to 15 medical centers. Preoperative imaging data, postoperative WSIs and clinical data will be collected and imported into the model to obtain predicted treatment regimens. No intervention will be implemented on actual clinical decisions in this phase. Researchers will record model prediction results and actual clinical decisions. Patients will be divided into the prediction-consistent cohort and prediction-inconsistent cohort according to whether the actual clinical decisions are consistent with model predictions. Long-term follow-up will be conducted to observe patients' actual prognosis, so as to evaluate the consistency between model predictions and actual outcomes, as well as the model's performance degradation in real-world settings.

(2) Study Population

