A multi-center collaboration model will be adopted for the prospective cohort. ① Prospective Observational Cohort: A total of 1,000 patients will be consecutively enrolled from 10 to 15 medical centers. Pathological slides will be collected for digital scanning, and preoperative imaging data will be imported into the model. No clinical intervention will be conducted; only model predictions and actual clinical outcomes will be recorded to evaluate the model's performance in real clinical settings. ② Prospective Interventional Cohort: A randomized controlled trial will be carried out in 3 to 5 medical centers with a planned enrollment of 600 patients. After obtaining patients' informed consent, patients will be randomly assigned to the intervention group (AI model-assisted decision-making) and the control group (standard clinical decision-making). Physicians in the intervention group will formulate treatment plans with reference to the optimal treatment regimens predicted by the AI model; the control group will receive routine treatment. Clinical outcomes will be compared between the two groups to provide high-level evidence for the clinical utility of the model.

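### The treatment decision change rate is calculated as disagreement between the AI and the physician's initial plan, so it does not measure changed decisions

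*Protocol*

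**What the plan says.** Protocol Section 3.3 describes the clinical-utility evaluation in the prospective phase as "focusing on evaluating the actual impact of the model on clinical decision-making and patient prognosis". Among its secondary clinical endpoints it gives "Treatment decision change rate, calculated as the proportion of cases where AI recommendations are inconsistent with" the physician's initial treatment plan. The only two inputs are the AI recommendation and the initial plan.

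The next endpoint in the same paragraph is "Physician adherence, defined as the proportion of physicians in the intervention group who finally follow AI recommendations".

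Two parts of Section 3.1 bear on how these should be read. In the randomised cohort, "Physicians in the intervention group will formulate treatment plans with reference to the optimal treatment regimens predicted by the AI model", so the AI output informs the plan but does not bind it. In the observational cohort, "No intervention will be implemented on actual clinical decisions in this phase", yet "Patients will be divided into the prediction-consistent cohort and prediction-inconsistent cohort" according to whether actual decisions match the model.

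No other section redefines the change rate, and Section 3.8 does not return to it.

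**The concern.** A decision has changed when the final plan differs from the initial one. The stated formula omits the final plan, so it describes the model and existing practice, not what physicians did after seeing the model's output. Because intervention-arm physicians are free to keep their initial plan, disagreement need not become change.

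If the rule is followed as written, a model whose advice is always set aside and a model whose advice is always taken get the same change rate, provided they disagree with initial plans equally often. For AI-prompted changes the error runs in one direction only: the reported figure equals or exceeds the true one. A report quoting it under its present name could overstate how far the AI altered treatment decisions.

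This is not a detail left for a statistical analysis plan. The protocol fixes the formula, and an analysis plan that follows it would carry the mismatch forward.

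**Working it through.** The protocol states no figure for this endpoint, so there is nothing to reproduce. The check is on the definition, with an illustration of size.

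**Inputs**
- Numerator of the rate: cases where the AI differs from the initial plan (Section 3.3).
- Intervention-arm size: 300 (Section 3.4.2), used only for the illustration.
- D, the share of cases in disagreement, and s, the share of those in which the plan is then changed: not in the protocol. D is set to 10%, 30% and 50%, and s to 0%, 50% and 100%, as assumptions.

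**Formulas**
- Protocol's rate = D, for every s.
- Decisions changed after AI disagreement = D × s.

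The second line equals *final plan different from initial plan* if plans that already agreed with the AI are left alone.

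**Results, 300 cases**

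| Assumed D | Protocol's rate, any s | True changes, s = 0% | True changes, s = 50% | True changes, s = 100% |
|---|---|---|---|---|
| 10% | 30 (10%) | 0 | 15 (5%) | 30 (10%) |
| 30% | 90 (30%) | 0 | 45 (15%) | 90 (30%) |
| 50% | 150 (50%) | 0 | 75 (25%) | 150 (50%) |

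For example, with D = 30% and s = 50%: 300 × 0.30 = 90 reported, and 90 × 0.50 = 45 actually changed. The two definitions agree only when s = 100% or D = 0.

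**A check from the protocol's own design.** In the observational cohort the AI is not allowed to influence decisions, so AI-prompted change is zero by design. Disagreement is nevertheless expected, since an inconsistent cohort is to be formed. The same comparison made there would give a non-zero change rate. Section 3.3 does not say that the rate will be reported for that cohort; the example only shows what the formula measures.

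**Can adherence recover the true rate?** Suppose adherence were counted per case, agreed plans never changed, and every change went to the AI's regimen. Then adherence a = (1 − D) + D × s, and the true rate would be D × s = a + D − 1. With D = 30% and s = 0, a = 70% although the AI influenced nothing; with s = 50%, a = 70% + 15% = 85%, and 85% + 30% − 100% = 15% is recovered. As written, however, adherence is a proportion of physicians. A physician treats several patients and may follow the AI in some of them only, so the per-case identity does not apply and the true rate cannot be derived.

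**The case against.** The strongest reply is that the two endpoints work as a pair: disagreement with the initial plan shows the scope for change, and adherence shows whether the advice was taken. A model that physicians ignored would show lower adherence, so the protocol is not blind to uptake. The calculation is also stated openly, so a careful reader can see what was counted. Both points stand and limit the severity. They do not rescue the definition, because adherence has the wrong unit and includes cases in which the AI agreed from the start.

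Two stronger readings are tempting and should not be made.

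- *That this endpoint alone carries the claim of impact, so the trial cannot show any.* The sentence on actual impact introduces the whole clinical-utility section and covers prognosis as well. RFS, OS, adherence, decision curve analysis and decision confidence all fall under it.
- *That Section 3.4.2 implies about 50% concordance in usual care, and hence a change rate near 50%.* A reader might take the observational control rate of 60%, the rate under HR 0.7 of 0.60^0.7 = 0.699, and the randomised control rate of 65%, and solve p × 0.699 + (1 − p) × 0.60 = 0.65 for p of about 0.50. This mixes assumptions from two separate studies. It also fails on the protocol's own figure for the AI-assisted arm: setting the right-hand side to 0.75 gives p = 0.15 / 0.099, about 1.5, which is impossible. And it would concern actual decisions, not initial plans. The protocol gives no value for D.

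**Conclusion.** The definition is wrong for its name. As written, the endpoint reports the rate of disagreement between the AI and the initial plan, and would show changed decisions even if no plan were changed. This follows from the wording alone and holds for any D above zero with s below 100%.

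The size depends on values the protocol does not give. Over the assumed D of 10% to 50%, the overstatement in 300 cases is 30 to 150 at s = 0 and 15 to 75 at s = 50%, on the assumption that plans which agreed with the AI are not changed.

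Severity is minor. This is a secondary endpoint for which Section 3.8 names no hypothesis test, and nothing in the RFS and OS analyses, the alpha or the sample size depends on it.

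**What to change.** In the intervention arm:

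1. Record the initial plan before the AI output is seen, and the final plan afterwards, for each case.
2. Define the treatment decision change rate as the proportion of cases whose final plan differs from the initial plan, split into changes towards and away from the AI recommendation.
3. Keep the present quantity, but report it as the *AI-physician initial disagreement rate*.

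The initial plan is already needed for the current formula, so the cost is one added eCRF field and, in all likelihood, a lower reported rate. It should be settled before enrolment, since a plan held before the AI output was seen cannot be reliably reconstructed later. If the extra field is not wanted, renaming the present measure would at least remove the mismatch, but the trial would then have no measure of changed decisions.

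A between-arm comparison is not needed to repair the definition. Split by direction, it would require AI output for control patients, and Section 3.1 plans none.
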